2 OBJECTIVES AND ENDPOINTS

Objectives	Endpoints	Justification for Endpoints
Primary		
Demonstrate that same-session MRI-only simulation and treatment with stereotactic MRI-guided radiotherapy (SMART) for spinal oligometastases is feasible by confirming that the first fraction of same-session MRI-only simulation and treatment with SMART can be delivered on the first on-table attempt for at least 70% of patients.	Delivery of the first fraction of same-session MRI-only simulation and treatment with SMART within the first on-table attempt for at least 70% of patients.	Clinically relevant
Exploratory		
1. Determine the average time (days) from patient consult appointment to successful delivery of the first treatment fraction.	Average time (days) from patient consult appointment to successful delivery of the first treatment fraction.	Clinically relevant
2. Determine the local, in-field tumor response and control rates at three months.	Local control rate Local in-field tumor response	Clinically relevant
3. Demonstrate that same-session MR-only simulation and treatment with SMART for treatment of spinal metastases will lead to comparable toxicities compared with historically reported rates using standard, CT-based SBRT assessed prospectively at three months post-treatment and retrospectively for later time-points.	CTCAE version 5, treatment related Grade 3 or higher toxicities	Clinically relevant
4. Determine the projected dosimetric differences between the study method of MRI-only planning using standard	Dosimetric differences between MRI-only planning using standard bulk density	Generation of preliminary data for

bulk density override dose calculations (which will be clinically used for all patients) and an exploratory alternative method of a novel voxel-by-voxel MRI-based dose calculation using an institutionally developed machine learning algorithm (which will be simulated for comparison but not used in clinical treatment planning).
	
override dose calculations and voxel-by-voxel MRI-based dose calculation using MLA
	
future radiation planning techniques.

5. Determine the on-table time required for same-session MR-only simulation and treatment with plan generation for the initial treatment fraction and for subsequent treatment fractions.
	
On-table time required for initial treatment fraction and subsequent treatment fractions
	
Clinically relevant

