5.3 Definitions of Evaluability

Endpoint	In order to be evaluable for this endpoint, a patient must have...
Primary: Feasibility	Received simulation
Exploratory: Time from consult to delivery of first fraction	Had a consult and received at least 1 fraction of RT
Exploratory: Local, in-field tumor response rates at 3 mos	Received any study treatment and undergone volumetric imaging at 3 mos
Exploratory: Local, in-field tumor control rate at 3 mos	
Exploratory: Grade 3 or higher toxicity	Received any study treatment
Exploratory: Dosimetric differences between MRI-only planning using standard bulk density override dose calculations and voxel-by-voxel MRI-based dose calculation using MLA	Received MRI and dose calculated using bulk density vs voxel-by-voxel
Exploratory: On-table time required for initial treatment fraction and subsequent treatment fractions	Received at least 1 fraction of RT

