5.6 Duration of Follow-up

Patients will have a single follow-up visit at 3 months post-end of treatment.

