5.7 Lost to Follow-Up

A participant will be considered lost to follow-up if he or she fails to return for the scheduled three-month follow up visit and is unable to be contacted by the study team.

The following actions must be taken if the participant fails to return to clinic for a required study visit:

- The study team will attempt to contact the participant and reschedule the missed visit within 3 days and counsel the participant on the importance of maintaining the assigned visit schedule and ascertain if the participant wishes to and/or should continue in the study.

- Before a participant is deemed lost to follow-up, the investigator or designee will make every effort to regain contact with the participant (where possible, 3 telephone calls and, if necessary, a certified letter to the participant's last known mailing address). These contact attempts should be documented in the participant's medical record or study file.
- Should the participant continue to be unreachable, he or she will be considered to have withdrawn from the study with a primary reason of lost to follow-up.

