8 STUDY CALENDAR

	Screening	Pre-Treatment	D1	D2	D3	D4	D5	3 mos post-SBRT ¹
Informed consent	X							
Medical history	X							
Volumetric imaging	X ⁵							X
Pregnancy test ²	X							
Adaptive SBRT			X	X	X ³	X ³	X ³	
Adverse events assessment		X	X -----X					

1. Window is 10-14 weeks post-completion of SBRT

2. Women of childbearing potential only; within 14 days of start of treatment

3. Treatment days 3,4,5 are for a 5-fraction course of treatment only. If a 2-fraction course is selected, then there would be only two treatment days.

5. Collection of a standard of care diagnostic CT scan completed in the past 6 months

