12.2 Sample Size Calculation

As a pilot study, the sample size is determined based on clinical considerations rather than statistical power. For our primary objective, our goal will be to report the description of same-session MR-only simulation and treatment with SMART treatment workflows, adaptation, and the time to delivery of first treatment fraction. Goal accrual will be 10 evaluable patients. For the secondary objectives, sample size is also based on clinical considerations rather than statistical power.

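### The 3-month local response rate, and apparently the control rate, rest only on patients who have the 3-month scan; no rule covers those without it, even if in-field progression is already documented

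*Combined protocol and SAP*

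**What the plan says.** Section 2 lists as an exploratory objective: "Determine the local, in-field tumor response and control rates at three months". Section 5.3 sets the evaluability condition for local response as "Received any study treatment and undergone volumetric imaging at 3 mos". The next row, "Exploratory: Local, in-field tumor control rate at 3 mos", has an empty condition cell in the text available to me. It looks like a merged cell that shares the response condition, but that is an inference.

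The scan is tied to one visit. Section 5.6 says "Patients will have a single follow-up visit at 3 months post-end of treatment", and a footnote to the Section 8 calendar says "Window is 10-14 weeks post-completion of SBRT". No earlier post-treatment imaging is scheduled. Under Section 5.7, a patient who cannot be reached is classed as follows: "he or she will be considered to have withdrawn from the study with a primary reason of lost to follow-up". That defines withdrawal and sets no denominator. Section 5.5 keeps patients who stop treatment early, for progression or any other reason, on the study calendar. Section 12.3 says only that exploratory aims are analysed at the end of the study. It gives neither a denominator nor a way to handle missing assessments.

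The target is stated in Section 12.2: "Goal accrual will be 10 evaluable patients". The reason given there is "As a pilot study, the sample size is determined based on clinical considerations rather than statistical power".

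**The concern.** The denominator depends on something that happens after treatment: being alive, in contact and scanned 10 to 14 weeks later. The population has metastatic cancer, eligibility goes down to KPS 60 (Section 3.1), and Section 12.1 expects some deaths unrelated to the trial. Some treated patients may therefore have no scan. If they are disproportionately those who failed in the treated field, the reported control rate describes a selected group.

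The sharpest case is a patient whose in-field progression has been documented and who then dies or is lost before the scan. The outcome is known, yet the rule as written leaves that patient out and nothing else brings the failure back in. The toxicity row of the same table already uses all patients who received any study treatment, so the narrower denominator is not forced by the design.

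Local response and control are the only tumour-outcome endpoints in Section 2. Section 12.3 refers in general terms to preserving the efficacy of standard spine SBRT when it describes what would support wider study.

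**Working it through.** **Figure to reproduce.** There is none. The target of 10 is not derived from a formula, and no precision, expected rate or dropout figure is given for these endpoints.

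**Inputs.**
- Patients treated: 10. This assumes that all 10 evaluable patients in Section 12.2 are treated; evaluability for the primary endpoint requires only simulation.
- True in-field control, p = 0.80. Section 1.2 gives roughly this value as background for SBRT of metastases, at up to four years. It is used here only for illustration.
- Number without a 3-month scan, and the scan probabilities: not in the documents. Assumed ranges are shown.

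**Step 1: direction of the bias.** Let r1 be the probability of a 3-month scan if locally controlled, and r0 the probability if failed in field. The expected imaged-only control rate is

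p_obs = p·r1 / [p·r1 + (1 − p)·r0]

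| r1 | r0 | Calculation | p_obs |
|---|---|---|---|
| 0.9 | 0.9 | 0.72 / (0.72 + 0.18) | 80.0% |
| 0.9 | 0.8 | 0.72 / (0.72 + 0.16) | 81.8% |
| 0.9 | 0.5 | 0.72 / (0.72 + 0.10) | 87.8% |
| 0.9 | 0.25 | 0.72 / (0.72 + 0.05) | 93.5% |
| 0.9 | 0 | 0.72 / 0.72 | 100% |
| 0.9 | 1.0 | 0.72 / (0.72 + 0.20) | 78.3% |
| 0.8 | 1.0 | 0.64 / (0.64 + 0.20) | 76.2% |

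The rate is too high only when r0 < r1. It is unbiased when the two are equal and too low when failures are scanned more often.

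**Step 2: the same in counts.** Suppose 8 of 10 are controlled and 2 have failed: 8/10 = 80% (exact 95% interval 44 to 98%).
- One failure unscanned: 8/9 = 89%.
- Both failures unscanned: 8/8 = 100% (63 to 100%).
- Two controlled patients unscanned instead: 6/8 = 75%.

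**Step 3: bounds when every scanned patient is controlled.** The worst case counts the unscanned as not controlled; the best case counts them as controlled.

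| Unscanned of 10 | Imaged-only | Worst case | Best case |
|---|---|---|---|
| 0 | 10/10 = 100% | 100% | 100% |
| 1 | 9/9 = 100% | 9/10 = 90% | 100% |
| 2 | 8/8 = 100% | 8/10 = 80% | 100% |
| 3 | 7/7 = 100% | 7/10 = 70% | 100% |
| 4 | 6/6 = 100% | 6/10 = 60% | 100% |

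With 3 unscanned, the Clopper-Pearson 95% intervals are 59 to 100% for 7/7 and 35 to 93% for 7/10.

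**Step 4: effect of counting a documented failure.** If one of those 3 unscanned patients has documented in-field progression, that outcome is no longer missing. The best case becomes 9/10 = 90% and the worst case stays at 7/10 = 70%. The imaged-only rule still gives 7/7.

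**The case against.** A reader might infer that any in-field progression before the scan is removed from the rate. The documents do not support that. Section 5.3 excludes for a missing scan, not for progression. Section 5.5 keeps early discontinuers on a calendar that includes the 3-month imaging, and Section 10.4.3 asks for objective progression to be documented after discontinuation for symptomatic deterioration. A progressor who is scanned is evaluable and can be counted as a failure. Since no earlier imaging is scheduled, documented progression with no later scan would come only from imaging outside the calendar, so such cases may be few.

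A reader might also infer that control must be biased upward. That does not follow either. Section 1.2 says most patients relapse at distant sites after SBRT for oligometastatic disease, and Section 12.1 expects unrelated deaths. Dropping patients who die with local control can leave the rate unchanged or lower it. For the same reason, counting every unscanned patient as not controlled is a worst-case bound and not an estimate.

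Three further points stand. The two intervals for 3 unscanned patients overlap widely, so 10 patients give an imprecise rate under either denominator. The monitoring tables in Appendix E record the number evaluable for each endpoint, each patient's 3-month response, vital status and cause of death, so missing patients would be visible, although no analysis rule follows. Section 12.3 mentions efficacy without naming local control or a threshold; its only numerical criterion is 70% first-attempt delivery.

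These arguments limit the size and direction of the problem. They do not supply the missing rule.

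**Conclusion.** The point holds in limited form. Section 5.3 conditions 3-month local response, and on a merged-cell reading local control, on having the scan. It can therefore leave out a patient already known to have failed in field. It also gives no account of patients who die, withdraw or are lost first.

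The direction of any bias in control cannot be settled from the documents. On the assumed scan probabilities, a true 80% would be reported as anything from 76% to 100%. With 10 treated and all scanned patients controlled, each unscanned patient lowers the worst-case rate by 10 percentage points while the imaged-only rate stays at 100%. For response, counting unscanned patients as non-responders gives the corresponding lower bound.

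The severity is minor: the endpoints are exploratory and descriptive, and the primary feasibility endpoint has its own denominator (patients who received simulation) and is untouched.

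**What to change.** In Section 5.3, with a matching sentence in Section 12.3:

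1. State the evaluability criterion for the local control row explicitly.
2. Count any documented in-field progression up to the 3-month assessment as a local failure, even if the 3-month scan is missing.
3. Report the number treated and the number imaged, and show deaths and losses without documented local failure on a separate line.
4. Give the imaged-only rate together with best-case and worst-case rates over all treated patients.

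The cost is a few more table lines and no additional visits or scans. One field may be needed on an existing form to mark progression as in-field: the Follow Up Form in Section 9 is scheduled only at 3 months, and the death-from-progression entry in Section 9.1 does not separate in-field from distant disease. The published figure may also look less favourable than the imaged-only rate alone.

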5.4 Women of Childbearing Potential

Women of childbearing potential (defined as women with regular menses, women with amenorrhea, women with irregular cycles, women using a contraceptive method that precludes withdrawal bleeding, and women who have had a tubal ligation) are required to have a negative pregnancy test within 14 days prior to the first fraction of SBRT.

Female patients are required to use two forms of acceptable contraception, including one barrier method, during the course of study treatment.

If a patient is suspected to be pregnant, SBRT should be immediately discontinued. In addition a positive urine test must be confirmed by a serum pregnancy test. If it is confirmed that the patient is not pregnant, the patient may resume dosing.

If a female patient becomes pregnant during therapy, the investigator must be notified in order to facilitate outcome follow-up.

5.5 Duration of Therapy

If at any time the constraints of this protocol are considered to be detrimental to the patient's health and/or the patient no longer wishes to continue protocol therapy, the protocol therapy should be discontinued and the reason(s) for discontinuation documented in the case report forms.

In the absence of treatment delays due to adverse events, treatment may continue for a total of 2 or 5 fractions of SBRT or until one of the following criteria applies:

- Documented and confirmed disease progression
- Death
- Adverse event(s) that, in the judgment of the investigator, may cause severe or permanent harm or which rule out continuation of study drug
- General or specific changes in the patient's condition render the patient unable to receive further treatment in the judgment of the investigator
- Suspected pregnancy
- Serious non-compliance with the study protocol
- Lost to follow-up
- Patient withdraws consent
- Investigator removes the patient from study
- The Siteman Cancer Center decides to close the study

Patients who prematurely discontinue treatment for any reason will still be followed as indicated in the study calendar.

5.6 Duration of Follow-up

Patients will have a single follow-up visit at 3 months post-end of treatment.

5.7 Lost to Follow-Up

A participant will be considered lost to follow-up if he or she fails to return for the scheduled three-month follow up visit and is unable to be contacted by the study team.

The following actions must be taken if the participant fails to return to clinic for a required study visit:

- The study team will attempt to contact the participant and reschedule the missed visit within 3 days and counsel the participant on the importance of maintaining the assigned visit schedule and ascertain if the participant wishes to and/or should continue in the study.

- Before a participant is deemed lost to follow-up, the investigator or designee will make every effort to regain contact with the participant (where possible, 3 telephone calls and, if necessary, a certified letter to the participant's last known mailing address). These contact attempts should be documented in the participant's medical record or study file.
- Should the participant continue to be unreachable, he or she will be considered to have withdrawn from the study with a primary reason of lost to follow-up.

6 DOSE DELAYS / DOSE MODIFICATIONS

There will be no dose delays or modifications permitted.

7 REGULATORY AND REPORTING REQUIREMENTS

The entities providing oversight of safety and compliance with the protocol require reporting as outlined below. Please refer to Appendix B for definitions and Appendix C for a grid of reporting timelines.

Adverse events will be tracked from start of treatment through the 3-month post-treatment follow-up visit. All adverse events must be recorded on the toxicity tracking case report form (CRF) with the exception of:

- Baseline adverse events, which shall be recorded on the medical history CRF
- Grade 1-2 AEs regardless of relatedness
- Grade 3-4 AEs that predate SBRT
- Grade 3-4 AEs that are not at least probably attributable to treatment

Refer to the data submission schedule in Section 9 for instructions on the collection of AEs in the EDC.

Reporting requirements for Washington University study team may be found in Section 7.1.

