5.2 Collection of AEs

For all patients, neurologic toxicities of concern include (but are not limited to) treatment-related spinal injury resulting in sensory alteration, muscle weakness, or neuropathic pain limiting self-care in activities of daily living. For patients receiving treatment to lower thoracic and lumbar spine sites, toxicities of concern also include (but are not limited to) gastrointestinal toxicities such as: severe pain, severe nausea or diarrhea, severe constipation, and/or gastrointestinal hemorrhage, stenosis, ulceration, fistula, perforation, etc. Patients undergoing treatment for thoracic metastases will additionally be assessed using the CTCAE v5.0 criteria for lung, esophageal (eg esophagitis), and cardiovascular toxicity. Regardless of treatment site, skin toxicity will be tabulated according to the CTCAE v5.0 criteria.

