9.1 Adverse Event Collection in the Case Report Forms

All adverse events that occur beginning with start of treatment (minus exceptions defined in Section 7.0) must be captured in the Toxicity Form. Baseline AEs should be captured on the Medical History Form.

Participant death due to disease progression should be reported on the Toxicity Form as grade 5 disease progression. If death is due to an AE (e.g. cardiac disorders: cardiac arrest), report as a grade 5 event under that AE. Participant death must also be recorded on the Death Form.

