12.3 Statistical Analysis Plan

Regarding toxicity, we will report descriptive statistics for acute toxicity at a three-month time point. Toxicity rates are anticipated to be identical to those of other linear accelerator based SBRT treatments. Because spine SBRT is a standard-of-care treatment that is not in and of itself investigational, further prospective toxicity assessments are not indicated. Given that no prior data exists for same-session MR-only simulation and treatment with SMART for spinal metastases, we will report descriptive statistics. As a pilot study we will establish these baseline parameters.

The primary objective is to demonstrate that same-session MRI-only simulation and treatment with stereotactic MRI-guided radiotherapy (SMART) for spinal oligometastases is feasible by confirming that the first fraction of same-session MRI-only simulation and treatment with SMART can be delivered on the first on-table attempt for at least 70% of patients.

Our principle objectives in this trial will be to determine the feasibility and safety of for same-session MR-only simulation and treatment with stereotactic MR-guided online-adaptive radiotherapy (SMART) for treatment of spinal oligometastatic disease. If we can successfully deliver the first treatment fraction at time of the first on-table treatment attempt in 70% of patients, while maintaining the safety and efficacy profile of standard spine SBRT, we will consider this study as having provided sufficient pilot data to support more widespread study of same-session SMART paradigm. The long-term goals will be to improve patient outcomes and care by reducing time to treatment, through an expedited radiotherapy delivery workflow for spinal SBRT.

All exploratory aims will be analyzed at the end of the study.

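### Section 7 keeps every Grade 1-2 event off the toxicity form, although Section 5.2 commits to a skin toxicity table and thoracic organ assessment with no grade floor

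*Combined protocol and SAP*

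**What the plan says.** Four parts of the combined protocol and SAP bear on this.

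- **Section 7** lists what stays off the toxicity form. The list includes "Grade 1-2 AEs regardless of relatedness" and "Grade 3-4 AEs that are not at least probably attributable to treatment". It also includes "Baseline adverse events, which shall be recorded on the medical history CRF".
- **Section 9.1** applies that list to data capture: "All adverse events that occur beginning with start of treatment (minus exceptions defined in Section 7.0) must be captured in the Toxicity Form". The schedule in Section 9 names no other form designated for toxicity.
- **Section 5.2** makes two commitments without a minimum grade. For everyone: "Regardless of treatment site, skin toxicity will be tabulated according to the CTCAE v5.0 criteria". Patients treated for thoracic metastases "will additionally be assessed using the CTCAE v5.0 criteria for lung, esophageal (eg esophagitis), and cardiovascular toxicity".
- **Section 12.3** says "we will report descriptive statistics for acute toxicity at a three-month time point", again with no grade given. The same section names safety alongside feasibility as a main objective. It also makes keeping the safety profile of standard spine SBRT part of the condition for taking the workflow further.

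The declared toxicity endpoint (Section 2), its evaluability row (Section 5.3) and the stopping rule (Section 12.1) are all set at Grade 3 or above.

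**The concern.** The collection rule is narrower than the commitments it has to serve. A skin table by CTCAE grade needs the low grades, and an assessment of esophageal or lung toxicity that is never entered below Grade 3 leaves nothing to summarise below Grade 3. The exclusion applies even when the event is clearly caused by treatment.

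A gap also opens at baseline. Baseline events go on the medical history form. If a Grade 1 symptom worsens to Grade 2 after treatment, the starting value is recorded but the change does not reach the toxicity form.

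At stake is how much a 10-patient pilot of a new workflow can say about safety. If only attributable events of Grade 3 or above are entered, the safety statement rests on a very small count, possibly zero. Treatment-related lower-grade events would be missing from the trial data even if clinicians saw them.

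**Working it through.** **1. Follow one event through the sections.** Take a treatment-related Grade 2 skin reaction that arises after the first fraction.

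| Section | Effect on this event |
|---|---|
| 5.2 | Falls within the skin table, which has no grade floor |
| 8 (study calendar) | Adverse event assessment is scheduled from before treatment to the three-month visit, so the event can be observed |
| 7 | Excluded from the toxicity form because it is Grade 1-2 |
| 9.1 | Exclusion repeated for data capture |
| 12.3 | Not available to the acute-toxicity description |

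The same path holds for Grade 2 esophagitis in a thoracic patient and for a Grade 1 baseline symptom that becomes Grade 2. An attributable Grade 3 event passes through every step, so the endpoint and the stopping rule receive their data.

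**2. How much Grade 3+ events alone can tell.** The plan has no figure to reproduce. Section 12.2 sets 10 evaluable patients on clinical grounds, and Section 12.3 says only that toxicity rates should match other linear-accelerator SBRT, without a number. I take n = 10, all treated, and assume a true per-patient rate p of attributable Grade 3+ toxicity.

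Chance of no event: P(0) = (1 − p)^10.

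| Assumed p | P(0) |
|---|---|
| 2% | 0.98^10 = 0.817 |
| 5% | 0.95^10 = 0.599 |
| 10% | 0.90^10 = 0.349 |

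- Zero is the single most likely count when p < 1/(n + 1) = 1/11 = 9.1%.
- Zero is more likely than not when p < 1 − 0.5^(1/10) = 6.7%.
- At p = 10%, P(1) = 10 × 0.10 × 0.90^9 = 0.387, which exceeds P(0) = 0.349, so one event is then the likeliest count.
- If 0 of 10 is observed, the exact two-sided 95% upper limit is 1 − 0.025^(1/10) = 30.8%.

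**3. What recording lower grades could add.** Let q be an assumed per-patient rate of recordable Grade 1-2 toxicity. The documents give none. The chance that at least one of 10 patients has such an event is 1 − (1 − q)^10: 65% at q = 10%, 89% at 20%, 97% at 30% and 99.9% at 50%.

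**The case against.** The best defence is that Section 7 was written to fit the declared endpoint. Sections 2, 5.3 and 12.1 all speak of Grade 3 or above, and Section 7 collects broadly that set. Section 12.3 adds a reason for collecting little: spine SBRT is already standard care, so it sees no need for further prospective toxicity assessment. Most of the other items in Section 5.2 are serious as worded, for example "severe pain, severe nausea or diarrhea, severe constipation", and the neurologic ones limit self-care. On this view only a wording mismatch about skin remains, and one sentence would cure it.

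Much of this stands, and it rules out several stronger readings that a reader might infer:

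- *The Section 12.3 toxicity description cannot be produced.* It can. That section names no grade, and a Grade 3+ summary is available from what is collected.
- *Section 5.2 promises tables for all organ toxicity.* It commits to tabulation for skin only; lung, esophageal and cardiovascular toxicity are to be assessed.
- *The toxicity table will most likely be empty.* This depends on a rate that the documents do not state, and it fails at 10%. The toxicity form may also hold deaths from progression, which Section 9.1 enters as Grade 5.
- *The 31% upper limit is caused by the exclusion.* It comes from having 10 patients. Recording lower grades would not change the Grade 3+ count or its interval.
- *Lower-grade events leave no trace.* The exclusion governs the case report form; source records may still hold them.

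The defence does not remove the conflict. The skin and thoracic sentences in Section 5.2 carry no grade floor. The standard-care argument in Section 12.3 accompanies the promise of an acute-toxicity description and does not withdraw it, and Section 1.5 calls this workflow novel. Section 7.2 asks that events exempt from expedited reporting still be captured electronically, but it concerns a list of reporting exceptions, while Section 9.1 expressly keeps the Section 7 exclusions.

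**Conclusion.** The point holds as an inconsistency between Sections 7 and 9.1 on one side and Section 5.2 on the other, with a consequence for how full the Section 12.3 description can be. Followed as written, the plan gives a skin table with no Grade 1 or 2 rows, no form-based account of thoracic organ toxicity below Grade 3, and no record on the toxicity form of low-grade worsening from baseline. The endpoint and the stopping rule are sound in this respect.

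The size of the loss cannot be fixed from the documents, because they give no toxicity rates. The 82%, 60% and 35% chances of no Grade 3+ event rest on assumed rates of 2%, 5% and 10% and on 10 treated patients. They show that Grade 3+ events alone are thin evidence at this sample size, not that the count will be zero. I also assume that the follow-up form, whose content is not described, does not collect Grade 1-2 toxicity. The change is worth making, but the primary feasibility result does not depend on it.

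**What to change.** - **Section 7 (and so 9.1):** exempt the Section 5.2 domains (neurologic, gastrointestinal, lung, esophageal, cardiovascular, skin) from the Grade 1-2 exclusion. At minimum, record Grade 2 events at least possibly related to treatment, and skin toxicity at all grades.
- **Section 12.3:** tabulate the worst grade per patient in each domain against that patient's baseline grade. Keep Grade 3 or above as the endpoint.
- **If the sponsor prefers the narrower collection:** state in Sections 5.2 and 12.3 that only attributable Grade 3+ toxicity will be tabulated and described. This resolves the contradiction but not the loss of information.

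The first option costs a few extra form lines for 10 patients at assessments already on the study calendar, plus a protocol amendment. The second costs only the amendment.
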